5.0 Investigational Plan

- 5.1 Overall Design: This is a pilot phase II exploratory study. It is a non-randomized study which will be carried out at Auxilio Mutuo Hospital and possibly at other institutions to be recruited.
- 5.2 We plan to enter a total of 100 200 patients with the expectation that at least 40-60 will be eligible for therapy with methylprednisolone in order to determine whether the risk of progressing to respiratory failure can be reduced by administering corticosteroids.
- 5.3 We assume that >50% of patients who meet the criteria for entry into this trial will develop respiratory insufficiency if left untreated.
- 5.4 If \leq 50% of patients with high risk develop respiratory failure we will consider the treatment as successful.

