3.0 Background and Rationale

The management of Covid-19 with mild manifestations has usually been conservative. Traditionally, treatment has consisted of observation at home provided there is no shortness of breath or evidence of pneumonia. Front line therapy with Hydroxychloroquine (Plaquenil) combined with Azithromycin has been used with preliminary positive results[1]. Plasma therapy has been successfully used in a small number of cases[2]. Vitamin C has also been utilized, although no definitive results are available[3].

Covid-19 is a triphasic disorder typified by a first infectious phase that lasts from the first onset of symptoms until 7-10 days later when it is followed by a second phase considered as the inflammatory or pulmonary phase with appearance of lung infiltrates which is later followed by a hyperinflammation phase characterized by Acute Respiratory Distress Syndrome (ARDS), shock and cardiac failure. For unclear reasons, patients do not always proceed to develop the second or third phase and are spontaneously cured after the first phase. Figure 1

Figure 1

Basics of COVID19 infections

[figure not shown]

5 Siddiqi & Mehra, J Heart Lung Transpl (2020). Epub ahead of print: https://doi.org/10.1016/j.healun.2020.03.012

This second phase is heralded by an elevation of certain serologic markers of inflammation such as IL-6, CRP, LDH and ferritin as well as D-dimers[4, 5]. See figure 2

It is not clear why some patients enter this second phase of the disease while others do not, but what is clear is that the second or inflammatory phase is caused by pulmonary macrophage activation with subsequent release of the inflammatory mediators. These molecules will damage the capillary-alveolar membrane eventually causing respiratory insufficiency. These are the patients that frequently will require ventilatory support and eventually most will die. This second and third phase are in great part due to activation of the patient's immune system while the first phase is mostly mediated by the viral infection itself.

Figure 2 *

*Red line represents patients who died while blue line represents survivors. The x axis represents number of days after onset of illness.

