4.0 Study Objectives and End Points

Primary Objective:

- 1- To decrease the rate of progression to hypoxemic respiratory failure in high risk patients with Covid-19, treated with prophylactic steroids during the first phase of the disease.
 - a. Hypoxemic respiratory failure is defined as:
 - 1. O_2 saturation of < 91% or pO_2 <60 on room air
- 2- To evaluate the rate of complications of patients observed without treatment.
 Complications include progression to respiratory failure or any other complication leading to hospitalization.

Secondary Objectives:

- 1. To determine % survival at 28 days from registration on this clinical trial
- 2. To determine if there is any improvement in inflammatory markers following treatment with corticosteroids.
- 3. To define the length of hospitalization
- 4. To determine the frequency of admissions to ICU.
- 5. To determine the percentage of patients who require ventilatory support.
- 6. To determine the rate of complications and progression to respiratory failure in patients with favorable features (i.e., those eligible for observation and not for therapy with methylprednisolone.)
 - a. To validate these results in an independent cohort of cases diagnosed as Covid-19 from our general hospital population.
- 7. We will evaluate the proportion of patients with clinical improvement, as defined by live discharge from the hospital, a decrease of at least 2 points from baseline on a modified ordinal scale (as recommended by the WHO R&D Blueprint Group), or both. [10]
 - 7.1 The six-point scale consists of the following categories:
 - (1) not hospitalized;

- (2) hospitalized, not requiring supplemental oxygen;
- (3) hospitalized, requiring supplemental oxygen;
- (4) hospitalized, requiring nasal high-flow oxygen therapy, noninvasive mechanical ventilation, or both;
- (5) hospitalized, requiring invasive mechanical ventilation, ECMO, or both; and
- (6) death.

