 - 6.4.3 D-dimer > 1 mg/L (1,000 ng/ml) before day 10.
 - 6.4.4 CRP > 10 mg/dL (100 mg/L) before day 10.
 - 6.4.5 LDH above normal before day 10.

- 6.4.6 Lymphopenia (absolute lymphocyte count <900) before day 10.
- 6.4.7 O₂ saturation <94% by pulse oximetry, but more than 91%, before day 10.
- 6.4.8 CT chest with evidence of infiltrate(s).
- 6.5 Interpretation of results of rapid and PCR molecular tests:
 - 6.5.1 Those with serological positive test but negative molecular PCR test will be analyzed based on the clinical context. See below.
 - 6.5.2 Those who present with at least 2 of the following typical symptoms of Covid-19 (cough, fever, dyspnea, diarrhea, anosmia) will be considered as likely cases of Covid-19 while those with one or less symptoms will be considered as unlikely cases but will still be considered evaluable. They will be analyzed separately.
 - 6.5.3 Those who are PCR positive and serology positive or negative will be considered as definitive cases.
- 6.6 The CALL score will be used in the analysis of all cases (11). This score represents a composite index based on presence of comorbidities, age >60, lymphopenia and elevated LDH. Those cases with a score >6 have greater than 50% risk for serious complications.
- 6.7 Simultaneous treatment will be allowed with the following drugs: remdesivir, hydroxychloroquine, azithromycin, vitamin C, doxycycline, colchicine, zinc and ivermectin. Patients who have received 1 single dose of dexamethasone or methylprednisolone will be eligible. **Their use is not considered as a basis for exclusion** from this trial.

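### The 5.4 success rule credits methylprednisolone against an untreated-rate benchmark whose background treatment is mismatched or undefined, although 6.7 allows eight other drugs

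*Protocol*

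**What the plan says.** All references are to the Protocol.

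- Section 5.1 gives the design: "It is a non-randomized study which will be carried out at Auxilio Mutuo Hospital".
- Section 5.2 plans the treated group "with the expectation that at least 40-60 will be eligible for therapy with methylprednisolone" and gives its purpose: "in order to determine whether the risk of progressing to respiratory failure can be reduced by administering corticosteroids".
- Section 5.3 supplies the comparator, with no source cited there: "We assume that >50% of patients who meet the criteria for entry into this trial will develop respiratory insufficiency if left untreated".
- Section 5.4 is the decision rule. If 50% or fewer "of patients with high risk develop respiratory failure we will consider the treatment as successful".
- Section 6.7 sets what may be given alongside: "Simultaneous treatment will be allowed with the following drugs: remdesivir, hydroxychloroquine, azithromycin, vitamin C, doxycycline, colchicine, zinc and ivermectin". That is eight drugs. Section 7.7 excludes patients receiving tocilizumab or plasma therapy.
- Section 3.0 says of one permitted pair: "Front line therapy with Hydroxychloroquine (Plaquenil) combined with Azithromycin has been used with preliminary positive results".
- Section 6.1 gives steroids only to patients who meet the high-risk criteria. The patients who are only observed are therefore low-risk and cannot serve as a control for the treated group.

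**The concern.** A single-arm rule against a fixed rate isolates the study drug only if the fixed rate describes the same kind of patient on the same background treatment. Here the rule is applied to patients on methylprednisolone plus any of eight other drugs, while the benchmark is worded for patients given nothing. If a permitted drug lowers the failure rate, 5.4 credits that reduction to methylprednisolone.

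This is bias in the comparator, which is separate from the sampling error of a small trial. It matters because 5.4 fixes in advance a declaration of success on a primary objective, and because section 3.0 does not treat all the permitted drugs as inert.

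**Working it through.** **Is there a figure to reproduce?** No. The protocol states no error rate, power or target failure rate, so the check asks how far the 5.4 rule can move through co-treatment alone.

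**Inputs from the protocol.** Success means a failure proportion of 50% or less (5.4). The treated number is 40–60 (5.2); 50 is used here. The untreated rate is given only as above 50% (5.3).

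**Assumptions, because the documents give no values.** Methylprednisolone has no effect. The true untreated rate p0 is 55% or 60%. A share s of patients receives co-treatment, with relative risk RR of 0.9 or 0.8.

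**Formula.** The true failure rate is p = p0 × (1 − s + s × RR). The chance of meeting the rule is P(X ≤ 25), with X binomial (50, p). For example, p0 = 60%, s = 1 and RR = 0.8 give p = 0.60 × 0.8 = 48%, and P(X ≤ 25) = 66%.

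The last column applies a stricter rule to the same cases: an exact one-sided 5% test against 50%. At n = 50 it allows at most 18 failures.

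| Co-treatment | p (p0 = 55% / 60%) | Meets 5.4 (≤25/50) | Meets stricter rule (≤18/50) |
|---|---|---|---|
| None | 55% / 60% | 28% / 10% | 0.5% / 0.05% |
| RR 0.9, half | 52.25% / 57% | 43% / 20% | 1.5% / 0.2% |
| RR 0.9, all | 49.5% / 54% | 58% / 33% | 3.8% / 0.8% |
| RR 0.8, half | 49.5% / 54% | 58% / 33% | 3.8% / 0.8% |
| RR 0.8, all | 44% / 48% | 84% / 66% | 16% / 5.9% |

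**Across the planned range of n.** With p0 = 60% and all patients co-treated at RR 0.8, the chance of meeting 5.4 is 66.0% at n = 40 and 67.0% at n = 60. With no co-treatment it is 13.0% and 7.5%.

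**Effect of a larger sample.** This depends on which side of 50% the true rate falls. At p = 54% the chance of false success falls from 33% at n = 50 to 14% at n = 200. At p = 48% it rises from 66% at n = 50 to 83% at n = 500.

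**The case against.** The strongest reply concerns the word *untreated*. Secondary Objective 6 describes the observed patients as those not eligible for methylprednisolone, so treatment in this protocol often means methylprednisolone. The benchmark may then be meant as the rate without steroids under usual care. That reading is plausible and it stands. A reader might infer from 5.3 and 6.7 that the two background treatments are known to differ; the documents do not support that much. But the protocol never adopts the milder reading and does not say which usual care the figure assumes, so the benchmark is then undefined. The same ambiguity covers Primary Objective 2, "To evaluate the rate of complications of patients observed without treatment": section 6.7 is not limited to steroid-treated patients, but the phrase may only mean without methylprednisolone.

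Three further points stand in part:

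- The size is assumed throughout. A remark about preliminary positive results is no effect estimate, and 7.7 removes two other therapies from the mix.
- A reader might infer that a larger trial always makes the error worse, or that a stricter cut-off gives no help. Neither holds. More patients worsen it only when co-treatment takes the true rate below 50%. The stricter rule cuts false success sharply, to 0.8%–16% when all patients are co-treated at RR 0.8–0.9, and the 16% is the worst of the cases shown. The bare 50% cut-off is a weakness in itself, at 28% or 10% with no co-treatment.
- An effect that cannot be attributed is the ordinary limit of a single-arm pilot, and tables by concomitant drug may sit in an analysis plan that is not shown. The absence of stratification is therefore not the finding. The benchmark, the rule and the allowed drugs are all fixed in the protocol, and a table elsewhere would not change what 5.4 declares.

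**Conclusion.** The point holds. Sections 5.2 to 5.4, read with 6.7, let the trial call methylprednisolone successful because of an effect that belongs to a co-treatment. The benchmark's background is mismatched on the literal reading and undefined on the milder one.

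With an inert steroid, 50 patients and assumed untreated rates of 55% / 60%, giving all patients co-treatment raises the chance of declared success by 30 / 23 points at RR 0.9 (28% to 58%; 10% to 33%). At RR 0.8 the rise is 56 points at either rate (28% to 84%; 10% to 66%). These figures rest on assumed rates, uptake and effects. They show how sensitive the rule is, and are not evidence that any permitted drug works. The flaw is worth correcting but not fatal to an exploratory pilot.

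**What to change.** 1. In 5.3, state the benchmark as the failure rate expected without methylprednisolone under the co-treatments that 6.7 allows, and give its basis. In 5.4, state that meeting the rule supports methylprednisolone given with allowed co-treatment, not methylprednisolone alone.
2. Record use and dates of each 6.7 drug for steroid-treated patients, and a yes/no per drug for observed patients. Section 6.1 largely limits data on observed patients to baseline labs and CT, so amend it to match.
3. Report the Primary Objective 1 failure rate with an exact 95% confidence interval, overall and split by any versus no 6.7 drug. Keep the split descriptive. Patients without co-treatment are not a random subset, since use of these drugs may follow severity, so their rate should not be tested against the untreated benchmark.

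The cost is a little extra data collection, a narrower conclusion and wide subset intervals: 10/20 failures give an exact 95% interval of 27–73%, against 36–64% for 25/50. No patient's care changes.

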An elevated interleukin-6 (IL-6) has been strongly associated with the need for mechanical ventilation (p=.00005). In addition, the maximal IL-6 level (cutoff 80 pg./ml) for each patient during disease predicted respiratory failure with high accuracy (p=.000005, AUC=0.98). The risk of respiratory failure for patients with IL-6 levels of \geq 80 pg./ml was 22 times higher compared with patients who have lower IL-6 levels[9].

In this protocol, we propose to identify patients with Covid-19 who are at very high risk of developing cytokine storm and consequently respiratory failure. The goal is to treat them early with corticosteroids in order to determine if we can avoid the cytokine storm.

Diagnosis of Covid-19 will be established by means of either the PCR molecular test or with the rapid serologic test or both (see figure 3 below). Cases who are IgG positive but IgM negative, will not be considered eligible unless they are positive by molecular PCR test.

In addition, we propose to identify a subset of patients with low risk of complications by analyzing their markers of inflammation as well as other prognostic variables. Due to the large number of cases currently admitted to our hospital, the situation now has reached a critical point. If we could generate data that can provide guidance as to which patients can be safely managed on an outpatient basis and which ones could be discharged with little risk of complications, it could help relieve this burden.

Figure 3

Test results		lts	Clinian Cinniff
PCR	IgM	IgG	Clinical Significance
+	-	-	Patient may be in the window period of infection.
+	+	.=	Patient may be in the early stage of infection.
+	+	+	Patient is in the active phase of infection.
+	-	+	Patient may be in the late or recurrent stage of infection.
-	+	-	Patient may be in the early stage of infection. PCR result may be false-negative.
-	_	+	Patient may have had a past infection, and has recovered.
-	+	+	Patient may be in the recovery stage of an infection, or the PCR result may be false-negative.

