6.0 Inclusion Criteria

- 6.1 All patients diagnosed with Covid-19 will be registered on the study regardless of their severity, but only those who meet high risk criteria will be treated with steroids. Those who do not meet the criteria will only be registered with no need to collect further data except baseline labs and CT chest. They should sign the consent form and the data manager can collect the rest of the information.
- 6.2 Male or female patients of 21 years or older diagnosed with Covid-19 by PCR or by rapid serological test will be eligible. Diagnosis of Covid-19 will be established by means of either the PCR molecular test or with the rapid serologic test or both. (see figure 3)

We have learned recently that some cases produce IgG very early and presence of IgG doesn't mean that infection is late. Those who are IgM positive but PCR negative, will be considered as "suspicious for Covid-19"; however, if their clinical presentation is typical for Covid-19, (see below) they will be counted as a positive diagnosis. Those who are IgM positive but PCR negative, for purposes of analysis will be divided as "polysymptomatic" (2 or more symptoms characteristic of Covid-19) or "not polysymptomatic". The symptoms considered as characteristic are fever, cough, dyspnea, myalgia, diarrhea, anosmia/dysgeusia, malaise, headache, abdominal pain, neurological symptoms (paresthesiae, delirium etc).

- 6.2 a. Patients who have negative Covid IgG and IgM but whose PCR results are not available yet and who have typical symptoms of Covid-19 (see section 6.2 above), or who have typical CT chest findings such as ground glass opacities, will be considered eligible. If PCR later on turns to be negative, the patient will be retrospectively considered as ineligible.
- 6.3 Eligible patients will be registered on study on or before 10 days from first onset of symptoms. Patients whose symptoms started > 10 days ago; but who are not in respiratory failure are eligible if they are still symptomatic.
- 6.4 In order to be treated with methylprednisolone, they must meet at least two of the following criteria on or shortly before day 10 (but not before day 7)

 from first onset of symptoms, in order to avoid treatment during viral phase; if two criteria are met before day 7, patient is eligible but treatment should not start before day 7 of illness:
 - 6.4.1 Serum IL-6 \geq 10 pg/ml before day 10.
 - 6.4.2 Ferritin> 500 ng/ml before day 10.

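### The >50% untreated rate that serves as the control for the single-arm success rule is not supported for the patients who are treated, so a success at 50% or below cannot by itself be credited to the steroid

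*Protocol*

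**What the plan says.** The design is non-randomized (Protocol 5.1). Three statements fix how success is judged.

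- **Benchmark (5.3):** "We assume that >50% of patients who meet the criteria for entry into this trial will develop respiratory insufficiency if left untreated". No citation or data accompany it.
- **Rule (5.4):** if 50% or fewer "of patients with high risk develop respiratory failure we will consider the treatment as successful".
- **Size (5.2):** the expectation is that "at least 40-60 will be eligible for therapy with methylprednisolone".

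Who is registered and who is treated are separate matters. Under 6.1, "All patients diagnosed with Covid-19 will be registered on the study regardless of their severity". Section 6.4 governs treatment: "In order to be treated with methylprednisolone, they must meet at" least two of eight listed items. Among them are a serum IL-6 of at least "10 pg/ml before day 10", LDH above normal, CRP above 100 mg/L, lymphopenia, oxygen saturation between 91% and 94%, and a CT infiltrate.

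The primary endpoint (4.0) is saturation below 91% or pO2 below 60 on room air.

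For CALL, 6.6 says: "Those cases with a score >6 have greater than 50% risk for serious complications". That score is to be used in the analysis of all cases; it is not one of the 6.4 items.

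**The concern.** In a single-arm trial the assumed untreated rate does the work of the control arm. If it is too high for the patients actually treated, the rule in 5.4 can be met whatever the drug does. If it is right or too low, the rule protects better. The reader therefore needs a reason to believe the figure for this population and this endpoint, and the protocol does not give one.

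What is at stake is the meaning of the word successful in 5.4. Without a supported benchmark, an observed rate at or below 50% could reflect the drug, the case mix under 6.4, or the concomitant drugs allowed in 6.7 (remdesivir among them).

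**Working it through.** **Step 1. Look for the source of 50%.** The figures in the protocol that might support it are these.

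| Place | Figure | Population | Event |
|---|---|---|---|
| 5.3 | >50%, assumed | those meeting the criteria for entry | respiratory insufficiency |
| 6.6 | >50% | CALL above 6 | serious complications |
| 3.0 | 22 times higher risk | maximal IL-6 of 80 pg/ml or more | respiratory failure |
| 3.0 | 52% | steroid given late, with ARDS | death |

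None is an absolute untreated risk of the section 4.0 event in patients meeting two of the eight 6.4 items. The CALL figure belongs to another selector and another event, and its citation (11) has no entry in a reference list that ends at 10. The IL-6 figure is a relative risk. The 52% is mortality in treated patients.

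No alpha, power or target rate is stated in the protocol, so neither 50% nor 40-60 can be re-derived from it. What can be computed is how the stated rule behaves.

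**Step 2. Behaviour of 5.4 with an inert drug.** Inputs: n = 40 and n = 60 (5.2), and success if failures X ≤ n/2 (5.4). The true untreated rate p is **assumed** over a range. With an inert drug, X ~ Binomial(n, p), and

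P(success) = Σ from x = 0 to n/2 of C(n, x) pˣ (1−p)ⁿ⁻ˣ.

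| Assumed p | P(X ≤ 20), n = 40 | P(X ≤ 30), n = 60 |
|---|---|---|
| 30% | 0.998 | >0.999 |
| 40% | 0.926 | 0.956 |
| 45% | 0.787 | 0.818 |
| 50% | 0.563 | 0.551 |
| 60% | 0.130 | 0.075 |

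Two faults show here. At exactly 50% the rule passes an inert drug more than half the time, because it uses a point estimate with no error bound. Below 50% the benchmark itself fails.

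**Step 3. Separate the two faults.** Require the exact (Clopper-Pearson) one-sided 95% upper limit to be below 50%. This is the same as P(X ≤ c | n, 0.5) ≤ 0.05.

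- n = 40: c = 14 (35.0%), upper limit 49.2%, P = 0.040. With 15 failures the limit is 51.7%.
- n = 60: c = 23 (38.3%), upper limit 49.8%, P = 0.046. With 24 failures the limit is 51.4%.

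Chance that an inert drug meets this stricter rule:

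| Assumed p | X ≤ 14 of 40 | X ≤ 23 of 60 |
|---|---|---|
| 50% | 0.040 | 0.046 |
| 45% | 0.133 | 0.182 |
| 40% | 0.317 | 0.451 |
| 30% | 0.807 | 0.937 |

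The bound cures the first fault and reduces the second without removing it.

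**Step 4. When would the treated group reach 50%?** Let s be the share of treated patients with CALL above 6. The cohort rate is s × r₁ + (1 − s) × r₀. With assumed risks r₁ = 60% and r₀ = 20%, a 50% cohort rate needs s = (0.50 − 0.20)/(0.60 − 0.20) = 0.75. With 70% and 30%, s = (0.50 − 0.30)/(0.70 − 0.30) = 0.50. Section 6.4 requires no such share.

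**The case against.** **The benchmark is not shown to be wrong.** A reader might infer that the treated group is at low risk and that 50% is therefore false. The documents do not support that. They give no untreated rate for the 6.4 population, 5.3 is openly an assumption, and the study is an exploratory pilot. At a true 60%, which is consistent with 5.3, the rule passes an inert drug only 13% / 7% of the time. This objection stands and limits the finding to lack of support.

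**The criteria are not all mild.** One might describe the 6.4 items as eight mild criteria. CRP above 100 mg/L, lymphocytes below 900 and saturation of 91-94% are not shown to be mild. Section 3.0 also says that rises in IL-6, CRP, LDH, ferritin and D-dimers herald the inflammatory phase. That is relevant support for five of the eight items, but it is qualitative and does not yield 50%.

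**The IL-6 comparison is not like with like.** It is tempting to set the 10 pg/ml of 6.4.1 against the 80 pg/ml of section 3.0 and call it one eighth of the evidence-based cut-off. Section 3.0 says that "the maximal IL-6 level (cutoff 80 pg./ml) for each patient during disease predicted respiratory failure with high accuracy". That is a peak over the illness, whereas 6.4.1 uses an early value.

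**Restricting the success test to CALL above 6 would not solve it.** That would borrow an untraceable figure for a different event and lose power. If 20 treated patients had CALL above 6 (an assumed number), the cut-off would be 5, met with probability 0.42 at a true treated rate of 30%. With 30 such patients it would be 10, met with probability 0.73.

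The pilot label does not answer the remaining point, because 5.4 still declares the treatment successful.

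**Conclusion.** The concern holds as a lack of support. Section 5.4 depends on a benchmark for which the protocol gives no basis in the treated population on the section 4.0 endpoint, and the rule has no error bound. Over assumed untreated rates of 40-50%, an inert drug would be called successful with probability 0.55 to 0.96 for 40-60 patients. At 60% this falls to 0.13 / 0.07. Which case applies cannot be known from the documents, so a success cannot be attributed to treatment unless the benchmark holds.

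These figures assume independent patients, a fully inert drug and 40 or 60 treated. They do not show that the true rate lies below 50%. Nor does the two-of-eight rule define entry to the study: 6.1 registers all Covid-19 patients, so the reference in 5.3 to entry criteria needs to be tied to 6.4.

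**What to change.** 1. **5.4:** call the result successful only if the exact one-sided 95% upper limit for the section 4.0 failure rate in all treated patients is below 50%: 14 or fewer of 40, or 23 or fewer of 60. Compute the limit for the number actually treated.
2. **5.3:** define the benchmark as the untreated rate of the section 4.0 event in patients meeting 6.4, and give its source. If there is none, state that crossing 50% does not by itself show a treatment effect.
3. **Supporting analyses:** report the baseline CALL distribution and the primary rate with exact confidence intervals for CALL above 6 and for CALL 6 or less. Keep the success test on all treated patients, and do not split at an IL-6 of 80 pg/ml.

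**Cost.** No new data, since 6.6 already plans CALL for all cases. The claim becomes harder to reach: at a true treated rate of 40%, the stricter rule is met with probability 0.317 / 0.451, against 0.926 / 0.956 under the present one. The conclusion is also worded more cautiously. The bound does not repair a benchmark that is too high, so items 1 and 2 are both needed.

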10.0 Primary Response Criteria for patients receiving methylprednisolone

10.0.1 Clinical complete response criteria require all the following:

10.0.1.1	No need for ventilatory support at any point
10.0.1.2	Not oxygen dependent by day 28 of registration
10.0.1.3	Alive by day 28 from registration on trial
10.0.1.4	CT chest with minimal or no evidence of disease by day 28
	from registration

10.0.2 Clinical partial response criteria require that 2 of the following be present by day 14 of therapy:

10.0.2.1	No need for ventilatory support at any point
10.0.2.2	Not oxygen dependent by day 28 from registration on trial
10.0.2.3	CT chest stable to improve over baseline by day 28 from
	registration

10.1 Secondary Response Criteria:

- 10.1.1 Decrease of at least 25% in anyone of the following markers, if elevated at baseline: IL-6, ferritin, D-dimer, CRP or LDH by day 14
- 10.1.2 Improvement of absolute lymphocyte count in those presenting with lymphopenia. Improvement is defined as increase by 25 % or more by day 14.

11 Data Management

- 11.1 Patients will be registered after obtaining signed consent form.
- 11.2 Registration will be performed at Auxilio Mutuo by calling [contact] [name].

12 Statistical Analysis

- 12.0 Analysis will focus in comparing pre-treatment and post treatment values.

 Results will be analyzed using the intent to treat principle which in this case means that those cases who receive at least one dose of methylprednisolone will be considered evaluable.
- **12.1** Evaluable cases are considered as those who have clinical data for at least 1 subsequent day.
- 12.2 Due to the small sample size, non-parametric tests for matched data will be used.

13.0 REFERENCES:

- 1. Gautret, P., et al., *Hydroxychloroquine and azithromycin as a treatment of COVID-19:* results of an open-label non-randomized clinical trial. Int J Antimicrob Agents, 2020: p. 105949.
- 2. Chen, L., et al., *Convalescent plasma as a potential therapy for COVID-19.* Lancet Infect Dis, 2020. **20**(4): p. 398-400.
- 3. Carr, A.C., A new clinical trial to test high-dose vitamin C in patients with COVID-19. Crit Care, 2020. **24**(1): p. 133.
- 4. Zhou, F., et al., Clinical course and risk factors for mortality of adult inpatients with COVID-19 in Wuhan, China: a retrospective cohort study. Lancet, 2020. **395**(10229): p. 1054-1062.

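### The success cut-off in section 5.4 sits on the boundary of the assumed untreated rate and ignores sampling error, so an ineffective treatment could pass with probability up to about one half

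*Protocol*

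**What the plan says.** Section 5.3 of the protocol sets the benchmark: "We assume that >50% of patients who meet the criteria for entry into this trial will develop respiratory insufficiency if left untreated". It gives no point value and no source. Section 5.4 sets the rule: if the observed share is no more than "50% of patients with high risk develop respiratory failure we will consider the treatment as successful". Section 5.2 gives the expected number treated and the purpose: "at least 40-60 will be eligible for therapy with methylprednisolone in order to determine whether the risk of progressing to respiratory failure can be reduced". The design has no randomised control: "It is a non-randomized study which will be carried out at Auxilio Mutuo Hospital". Patients who do not meet the high-risk criteria are observed untreated, so they are not a comparator for the treated group.

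The endpoint is binary. Section 4.0 defines hypoxemic respiratory failure by "saturation of < 91% or pO_2 <60 on room air". Section 12 plans pre/post comparisons and says "Due to the small sample size, non-parametric tests for matched data will be used". Its analysis set is that "those cases who receive at least one dose of methylprednisolone will be considered evaluable". The protocol attaches no significance level, power, target treated rate or confidence limit to the rule in 5.4.

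**The concern.** The no-effect rates that 5.3 allows start immediately above 50%, and success starts at 50%. No gap separates the two, and the rule uses the observed proportion as if it were the true rate. With 40 to 60 patients the observed proportion can easily miss the true rate by ten percentage points or more. A result that shows no reduction at all can therefore be labelled a success.

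With no concurrent control, 5.4 is the only rule stated for the respiratory-failure part of the primary objective. If it cannot separate an active treatment from an inactive one near its own benchmark, the study cannot do what 5.2 says it is for.

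**Working it through.** The protocol gives no error rate, power or sample-size derivation, so there is no figure of its own to reproduce.

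**Inputs.** Number treated n = 40, 50, 60 (section 5.2). Success if failures X ≤ n/2 (section 5.4). Untreated rate p above 50%, value not given (section 5.3), so a range is shown.

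**Step 1: chance of declaring success when treatment changes nothing.** X ~ Binomial(n, p), and the chance is P(X ≤ n/2 | p).

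| True rate p | n = 40 | n = 50 | n = 60 |
|---|---|---|---|
| 50% (limit of 5.3) | 56.3% | 55.6% | 55.1% |
| 51% | 51.2% | 50.0% | 48.9% |
| 52% | 46.1% | 44.3% | 42.8% |
| 55% | 31.6% | 28.4% | 25.8% |
| 60% | 13.0% | 9.8% | 7.5% |
| 65% | 3.6% | 2.1% | 1.2% |
| 70% | 0.6% | 0.2% | 0.1% |

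For even n an exact tie counts as success, which is why the first row exceeds one half. For odd n (41, 51, 59) the chance is exactly 50.0% at p = 50%, and 39.8%, 38.7% and 37.9% at p = 52%. At p = 50%, adding patients leaves the chance near one half, because the cut-off equals the true rate.

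**Step 2: what a borderline success shows.** Exact two-sided 95% intervals: 20/40 gives 33.8% to 66.2%; 30/60 gives 36.8% to 63.2%. Both count as success, and both are compatible with no effect or with harm relative to 50%.

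**Step 3: a cut-off that allows for sampling error.** Take the largest c with P(X ≤ c | p = 0.5) ≤ 0.05. This is the same as requiring the one-sided 95% Clopper-Pearson upper limit to be below 50%.

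| n | c | Upper limit at c | Upper limit at c + 1 | Error at p = 50% |
|---|---|---|---|---|
| 40 | 14 | 49.2% | 51.7% | 4.0% |
| 50 | 18 | 48.6% | 50.6% | 3.2% |
| 60 | 23 | 49.8% | 51.4% | 4.6% |

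**Step 4: power of that cut-off,** P(X ≤ c | treated rate). The documents give no target treated rate, so these rates are assumptions.

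| Assumed treated rate | n = 40 | n = 50 | n = 60 |
|---|---|---|---|
| 30% | 81% | 86% | 94% |
| 35% | 57% | 62% | 75% |
| 40% | 32% | 34% | 45% |

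**The case against.** A reader might infer that, under the plan's own assumption, a useless treatment passes about half the time. The documents do not support that. Section 5.3 gives a floor, not a rate just above 50%. If the untreated rate were 65% or more, the false-success chance would be under 4%. The 55-56% figure also belongs to exactly 50%, which the strict inequality excludes, and to even numbers of patients. What remains is that the plan commits to nothing above the floor, so the floor is the proper place to evaluate the error. The entry criteria do not supply a higher rate either: any two of the eight items in section 6.4 suffice, including LDH merely above normal. The CALL-score figure in section 6.6 concerns serious complications, and the score is not required for treatment.

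The study is labelled a pilot and exploratory, so a lenient screen does less harm than in a confirmatory trial. That is fair and softens the consequence. But 5.4 still promises a verdict of success rather than an estimate.

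A SAP might add detail. Here, though, the rule is fixed in the protocol itself, and the matched pre/post tests in section 12 do not compare a failure proportion with 50%.

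Finally, a stricter cut-off still tests against an unsourced 50%. If the untreated rate were really 30% (an assumption), the revised rule would pass an ineffective treatment 81%, 86% or 94% of the time at n = 40, 50 or 60. This objection stands in full and limits what the fix can claim.

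**Conclusion.** The point holds as a worst-case statement. The cut-off in 5.4 is the boundary of the no-effect rate in 5.3, with no allowance for sampling error. The chance of declaring an ineffective treatment successful can therefore be as high as about one half, and it falls quickly if the untreated rate is well above 50%. The calculation assumes independent patients, 40 to 60 treated, and a treatment that leaves the failure rate unchanged.

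The rule as written cannot establish that the risk is reduced. This does not show that the true error is one half, that the untreated rate is near 50%, or that the treatment is ineffective. The benchmark also has a wording problem: 5.3 speaks of respiratory insufficiency and 5.4 of respiratory failure, and only the latter is defined, so the two may not be the same event.

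**What to change.** Replace 5.4 with: *The treatment is considered promising if the upper limit of the one-sided 95% exact (Clopper-Pearson) interval for the respiratory-failure rate among treated patients is below 50%.* Apply it at the number actually treated; 14/40, 18/50 and 23/60 are examples of the largest passing counts. Report the rate with its two-sided 95% interval whatever the outcome. Other exact or near-exact one-sided methods would also serve, provided the choice is fixed in advance.

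The change is one sentence, with no extra patients and no change to care. The cost is a stricter bar. Only a large effect, to a failure rate of about 30%, is well powered at 40 to 60 patients, and the plan should say so.

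The change controls sampling error only. It neither supports the 50% benchmark nor replaces a concurrent control. The protocol should therefore give the source of the benchmark, or state that it has none, use one term for the event in 5.3 and 5.4, and describe a positive result as promising rather than as proof of a reduction.
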